### Outcomes.

Primary efficacy outcome. The primary endpoint for this study will be improvement in improvement in 0-10 pain score between medication administration and 90 minutes later.

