## IV lidocaine v. hydromorphone for acute abdominal pain. A randomized trial. Version date 07112018

## Methods.

Study design. This will be a randomized, double blind, comparative effectiveness study conducted in two Montefiore EDs. Outcomes will be assessed through out the ED stay and by telephone 7 days later. Ethical oversight will be provided by the Montefiore Medical Center IRB. This trial will be registered online at <http://www.clinicaltrials.gov>.

Population of interest. Eligible patients are those who present to an ED for treatment of acute abdominal pain. Acute will be defined as pain for no more than seven days. At the time of enrollment, the ED treatment plan must include use of an intravenous opioid. Adults aged at least 18 years and less than 65 years will be eligible to participate. Patients will be excluded from participation if they have cardiac conduction system impairment (QTc duration > 0.5s, QRS duration > 0.12s, or PR interval duration > 0.2s), known renal (CKD >2) or liver disease (Childs-Pugh B or greater), are hemodynamically unstable, as determined by the attending physician, are pregnant or breastfeeding, or have a known allergy to either medication. Patients will also be excluded if they have used prescription or illicit opioids within the previous week, or if they have a chronic pain disorder, defined as use of any analgesic medication on more days than not during the month preceding the acute episode of pain. Patients weighing < 60kg or > 120kg will be excluded.

Study setting. This study will be conducted in the Moses and Weiler EDs.

Investigational medications. Patients will be randomized in a 1:1 ration to one of the following study arms:

- A. Lidocaine: 120mg IV
- B. Hydromorphone: 1mg IV

Each of these medications will be administered as an intravenous drip over 10 minutes. If patients report insufficient relief of pain at 30 minutes, they will be eligible for a second dose of the same medication. Thirty minutes after the investigational medication was initiated, participants will be asked, "Do you want another dose of the same medication to treat your pain?" Subjects who reply affirmatively will be administered the same medication and dose they had received thirty minutes previously. Patients who require additional medication beyond one hour will be administered medication at the discretion of the treating clinician.

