## IV lidocaine v. hydromorphone for acute abdominal pain. A randomized trial. Version date 07112018

arms of the trial, research subjects and research personnel will be asked, at the time of ED discharge, to guess which medications were administered.

**Stratification.** Subjects will be stratified by study site (Moses or Einstein) and diagnosis (presumptive diagnosis of kidney stones versus non-kidney stone presumptive diagnosis). The rationale for stratification based on presumptive diagnosis of kidney stones is two-fold: 1) kidney stones represent a large subset of abdominal pain diagnoses; 2) kidney stones may be more likely to respond to IV lidocaine than other causes of abdominal pain

**Details of protocol.** Patients who present to our ED with acute abdominal pain will be referred by the attending emergency physician to the research staff for enrollment. Because of the severity of pain, only those who can appropriately make an informed decision about participating will be enrolled (those who cannot will be screened and excluded). Eligibility will be ascertained by research associates and verified by the site investigator. An EKG will be performed and interpreted by the attending physician. A point-of-care urine pregnancy test will be performed. Capacity to consent to participate in this study will be assessed by the attending emergency physician and documented. Masked medication will be obtained from the pharmacy. The research associate will perform a baseline pain assessment. Prior to the administration of any medication, patients will be placed on a cardiac monitor with telemetry where they will have continuous measurement of their heart rate and oxygenation. Blood pressure will be measured every 15 minutes for the first hour. The ED nurse will administer the research medication as described above. Research associates will perform an assessment of pain and adverse events every 30 minutes. Use of off-protocol medication to treat pain or associated symptoms will be recorded. Seven days after enrollment, patients will be contacted by telephone to determine satisfaction with the medication, course of pain subsequent to the ED visit, and occurrence of any adverse events.

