### Secondary efficacy outcomes.

- 1) Sufficient pain relief, defined as no need for off-protocol parenteral pain medication during the ED visit. The following parenteral medications will be considered off protocol pain medication: any opioid, any non-steroidal anti-inflammatory drug
- 2) Improvement in numerical pain scores 15, 30, 90, 120, and 180 minutes after investigational medication

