### Sample size calculation.

Based on previous work, we anticipate a mean improvement in 0-10 pain score of 4.9 and a standard deviation of 2.8. Using a between-group difference of 1.3 as a minimum clinically significant difference, an alpha = 0.05 and a beta = 0.20, we determined the need for 73 patients in each group. We will enroll 105% of this N in anticipation of protocol violations and missing data, thus leaving us with a sample size of 154 patients. With 73 patients in each arm, the sample size is sufficiently robust that the ttest can be used even if the data are not normally distributed (central limit theorem).

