### Analysis.

Baseline characteristics will be reported as mean (SD), median (IQR), or n/N (%), as appropriate. The primary outcome, improvement in 0-10 pain score between baseline and one hour will be reported as mean (95%CI) for each group. The between-group difference in mean improvement in 0-10 pain score will be calculated with 95%CI. If this 95%CI does not cross zero, the results will be considered statistically significantly different. All dichotomous values will be reported as proportions with 95%CI. For formal statistical testing, we will use the ttest.

We will use an intention to treat analysis. Once an investigational medication is initiated, the patient will be included in the analysis, regardless of whether or not the patient completed the medication infusion and regardless of whether or not the patient requests off-protocol analgesic medication.

**Data collection and processing.** Data acquisition will be performed using REDCap (Research Electronic Data Capture), a secure, web-based application designed specifically to support data capture for research studies. The REDCap project (<http://project-redcap.org/>) is an international project, with more than 70 institutional partners from CTSA and GCRC funded institutions. Paper consent documents will be maintained in locked research cabinets.

**Data monitoring committee and interim analysis.** This committee will be headed by [name], PhD, an epidemiologist and include [name], MD, the director of the Moses ED. The committee will meet every month with the PI to 1) monitor adverse events and develop strategies to minimize these; and, 2) monitor recruitment and enrollment. Because our goal is to report the results with sufficient precision to influence clinical practice, we will not perform an interim efficacy analysis.

**Registration.** The study will be registered at <http://www.clinicaltrials.gov>.

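### The primary endpoint is set at 90 minutes in the Outcomes section but at one hour in the Analysis section, so two different results could each be called the planned primary

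*Combined protocol and SAP*

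**What the plan says.** The current version (07112018) describes the timing of pain scores in several places:

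- **Outcomes, primary efficacy outcome:** the endpoint is "improvement in 0-10 pain score between medication administration and 90 minutes later".
- **Analysis:** "The primary outcome, improvement in 0-10 pain score between baseline and one hour will be reported as mean (95%CI) for each group". The same paragraph then gives the decision rule: the difference counts as significant if its 95% confidence interval excludes zero.
- **Secondary efficacy outcomes, item 2:** "Improvement in numerical pain scores 15, 30, 90, 120, and 180 minutes after investigational medication". Ninety minutes is listed; 60 minutes is not.
- **Details of protocol:** "Research associates will perform an assessment of pain and adverse events every 30 minutes". Scores at 60 and at 90 minutes are therefore both scheduled.
- **Investigational medications:** a second blinded dose is offered at 30 minutes. After that, "Patients who require additional medication beyond one hour will be administered medication at the discretion of the treating clinician".
- **Analysis, intention-to-treat paragraph:** treated patients are kept in the analysis "regardless of whether or not the patient requests off-protocol analgesic medication".
- **Sample size calculation:** "we anticipate a mean improvement in 0-10 pain score of 4.9 and a standard deviation of 2.8". No time is attached to these figures or to the target difference of 1.3.

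**The concern.** A trial with one primary endpoint and one decision rule needs one time point. Here the section that defines the endpoint and the section that analyses it name different times, and both scores will be available under the assessment schedule. If the two contrasts disagree, either could be reported as prespecified, and the nominal 5% error rate would no longer hold. Even if nobody selects, a reader cannot tell which result is confirmatory.

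The times also measure different things. Clinician-chosen analgesia becomes available between them, so the 90-minute score can include its effect to a degree that the one-hour score should not. If one arm needs more of it, the 90-minute difference could shrink towards zero.

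A related, smaller conflict is that the secondary list calls for a 15-minute pain score, while the stated pain assessments are half-hourly. The only 15-minute schedule given is for blood pressure. Read strictly, the schedule yields no 15-minute pain data.

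**Working it through.** **1. Is the conflict only in the start point?** No. One section counts from medication administration and the other from baseline, but Details of protocol puts the baseline pain assessment before dosing, so the two starts are effectively the same. The end times differ by 90 − 60 = 30 minutes.

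**2. Does the secondary list settle it?**

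| If the primary is at | 90 minutes in the secondary list | 60 minutes |
|---|---|---|
| 90 minutes (Outcomes) | duplicates the primary | in no outcome list |
| 60 minutes (Analysis) | a proper secondary time | primary, correctly absent from the list |

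The list fits a one-hour primary better. That is an inference, and it contradicts the section that defines the endpoint.

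**3. Does the sample size settle it?** Inputs from the Sample size calculation: difference 1.3, SD 2.8, alpha 0.05 (taken as two-sided), power 0.80, two equal groups.

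n per group = 2 × SD² × (z₀.₉₇₅ + z₀.₈₀)² / difference²

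= 2 × 7.84 × (1.960 + 0.842)² / 1.69 = 72.82, rounded up to 73.

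This matches the plan, with power 80.1%. The exact t-test version gives 73.8, and a one-sided test would need only 58, so two-sided is the right reading. For the total, 2 × 73 = 146 and 146 × 1.05 = 153.3, rounded up to the stated 154. The calculation is sound, but because its inputs carry no time it cannot show which endpoint was meant.

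**4. What does an open choice cost?** Let Z₁ and Z₂ be the test statistics at 60 and 90 minutes under no treatment difference, bivariate normal with correlation ρ. If either may be called primary, the false-positive rate is

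1 − P(|Z₁| ≤ 1.96 and |Z₂| ≤ 1.96).

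The documents give no ρ, so a range is shown:

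| ρ (assumed) | False-positive rate |
|---|---|
| 0 (independent; 1 − 0.95²) | 9.75% |
| 0.5 | 9.07% |
| 0.6 | 8.75% |
| 0.7 | 8.35% |
| 0.8 | 7.81% |
| 0.9 | 7.04% |
| 0.95 | 6.46% |

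Two pain scores from the same patient 30 minutes apart should be clearly correlated, so 0.5 to 0.9 is taken as the working range: 9.1% down to 7.0%. With one time fixed in advance the rate returns to 5%, and the 73 per group and 80.1% power stand, provided that the SD of 2.8 and the difference of 1.3 apply at that time.

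**The case against.** The strongest reply is that this is a drafting slip rather than an open choice. The primary-outcome sentence has another editing error (a repeated phrase), the decision rule is attached to one hour only, and the secondary list looks as if it was written for a one-hour primary. On that view the repair is a one-word correction, and the inflated error rate describes selective reporting that nobody has proposed. This is partly right. The 7.0% to 9.1% is conditional on a choice made after seeing the data, and it falls to 6.5% at a correlation of 0.95. But the documents do not show which sentence contains the slip, and a primary endpoint should not be left to inference. The plan also commits to public registration, and that record might name one time; it was not available here, and it would not make the two sections agree.

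A second reply is that 60 minutes is not clearly the better choice. The plan does not bar off-protocol analgesia in the first hour, so the one-hour score is not guaranteed to be free of it. And "If patients report insufficient relief of pain at 30 minutes, they will be eligible for a second dose of the same medication": with a 10-minute infusion begun promptly, that dose ends at about 40 minutes, which leaves roughly 20 minutes before a one-hour score and 50 before a 90-minute one. A 90-minute endpoint can be defended for a two-dose strategy. This stands as a reason to leave the choice to the sponsor; it is no reason to leave both times in the plan.

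Finally, the 15-minute score can be read as an extra assessment on top of the half-hourly schedule. That is possible, and the point is a clarification that does not carry the weight of the primary-endpoint conflict.

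**Conclusion.** The concern holds. The primary endpoint has two different times in the current text of one version, no section resolves the difference, and the single significance rule depends on it. If the choice stays open until results are known, the two-sided false-positive rate is about 7.0% to 9.1% instead of 5% (7.8% at a correlation of 0.8). That range assumes a correlation of 0.9 to 0.5 between the two test statistics and that either result could be reported as primary; it illustrates the exposure and is not an estimate of what the trial will do. The contradiction itself needs no assumption. It must be corrected, because a correction made after unblinding could not be shown to be independent of the results.

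**What to change.** State one primary time, in the same words, in the Outcomes and Analysis sections. Either choice is workable:

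- **60 minutes:** change the primary-outcome sentence in Outcomes. The Analysis section and the secondary list then stand. This is the last scheduled score before clinician-chosen medication opens.
- **90 minutes:** change the Analysis section, and replace 90 with 60 in item 2 of the secondary list. State that the contrast includes the effect of any medication given after the first hour.

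In the Sample size calculation, say to which time the improvement of 4.9, the SD of 2.8 and the difference of 1.3 refer. Also add a 15-minute pain score to Details of protocol, or delete 15 minutes from the secondary list.

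The cost is a wording amendment, dated before unblinding, with any registered time frame checked against it. The sample size does not change if its inputs apply at the chosen time, and no new assessment is needed for the primary, since both scores are already scheduled. Adding a 15-minute score, if that option is taken, means one more brief assessment per patient.

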### Secondary efficacy outcomes.

- 1) Sufficient pain relief, defined as no need for off-protocol parenteral pain medication during the ED visit. The following parenteral medications will be considered off protocol pain medication: any opioid, any non-steroidal anti-inflammatory drug
- 2) Improvement in numerical pain scores 15, 30, 90, 120, and 180 minutes after investigational medication

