## Background

Intravenous opioids are commonly used to treat acute abdominal pain in US emergency departments (ED). These medications are highly efficacious and, when used in a monitored setting such as the ED, extremely safe. Use of opioids has fallen out of favor because of a spike in opioid-related overdose deaths throughout the US. While use of opioids in the ED is unlikely to contribute to outpatient opioid deaths, minimizing the use of opioids in the ED will contribute to an opioid free culture, in which opioids are used only when absolutely necessary. A variety of different types of medications can be used in lieu of opioids. One such medication, intravenous lidocaine, has been used extensively in various arenas including the operating room, where it is an evidence-based preventive of post-operative pain, and the cardiac care unit, where it historically had been used to prevent arrhythmias. Some data suggest that it may be efficacious for acute abdominal pain as well.

Intravenous lidocaine has long been used to treat pain. In publications dating back to 1980, intravenous lidocaine has been shown to be an effective treatment for neuropathic pain (2). In the post-operative setting, intravenous lidocaine decreased pain and decreased the need for opiates (3-7). More recently, emergency medicine investigators in Iran, demonstrated that intravenous lidocaine decreased pain associated with renal colic and limb ischemia (9-11). An ED-based study in the US showed comparable efficacy between morphine and intravenous lidocaine when used for acute abdominal pain (12).

Over the years, intravenous lidocaine has been used for a variety of indications including arrhythmia prophylaxis in patients with acute coronary syndromes. Known side effects of intravenous lidocaine range from transient neurological symptoms (dizziness, paresthesias), to cardiac dysrhythmias and seizure. To date, no deaths have been attributed to its use for treating pain and the only documented significant complication was due to an unintentional overdose where a patient received ten times the normal dose (2, 3, 8). All reported side effects in pain patients have been transient and resolve by stopping the drug, decreasing the infusion rate, or by observation alone. Thus, intravenous lidocaine is an emerging medication for safe and rapid relief of pain, has no known addictive properties, and creates a potential for a pain practice paradigm shift in the United States.

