We therefore propose a randomized, double blind, RCT to address the following aim:  
To determine the relative efficacy and safety of IV lidocaine among patients with acute abdominal pain, when compared to IV hydromorphone, the putative standard of care

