Hydromorphone, dosed at 1mg + 1mg, is a safe and effective strategy for management of acute pain in the ED (<https://www.ncbi.nlm.nih.gov/pubmed/21507527>). The optimal dose of IV lidocaine for acute pain is unknown. For this study, we chose a dose that was most likely to be efficacious while minimizing potential for adverse events. A Cochrane review of intravenous lidocaine for post-operative pain reported that most trials used lidocaine boluses between 1-3 mg/kg (typically 1.5 mg/kg). ED-based studies have used doses of 1.5-2 mg/kg (8-11).

Assignment. Will be concealed. The research pharmacist will determine assignment based on a random number sequence.

Randomization. Randomization will occur in blocks of four based on a random number generator.

Blinding. Research subjects, clinicians, and research personnel will be blinded. To assess the success of blinding, which may be threatened by the occurrence of certain medication side-effects unique to particular

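### Secondary outcome 1 counts only parenteral opioids and NSAIDs as rescue, so a patient rescued only with another parenteral analgesic is scored as having sufficient relief (minor, cheap to close)

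*Combined protocol and SAP*

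**What the plan says.** All references are to the combined protocol and SAP.

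- **Secondary efficacy outcomes, item 1** states the concept: "Sufficient pain relief, defined as no need for off-protocol parenteral pain medication during the ED visit". The next sentence says what counts: "The following parenteral medications will be considered off protocol pain medication: any opioid, any non-steroidal anti-inflammatory drug". Nothing in it marks the two classes as examples, and there is no residual category for other analgesics.
- **Methods, Investigational medications**, on care after the protocol doses: "Patients who require additional medication beyond one hour will be administered medication at the discretion of the treating clinician". No drug class is named or excluded.
- **Details of protocol**: "Use of off-protocol medication to treat pain or associated symptoms will be recorded". Recording is not limited by class. The section does not say whether the reason for giving each drug is captured.
- **Secondary efficacy outcomes, item 4** is a separate outcome for drugs given for associated symptoms, with anti-nausea drugs and anti-histamines as its examples. It does not cover other analgesics.
- **Background**: "A variety of different types of medications can be used in lieu of opioids". The example it then gives is IV lidocaine, presented as a treatment for pain.
- **Analysis** reports dichotomous outcomes as proportions with 95% confidence intervals. It sets no second definition of this outcome.

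**The concern.** The concept and the scoring rule do not have the same reach. The concept is any parenteral analgesic rescue outside the protocol; the rule detects two classes of it. A patient who needed rescue and received only a parenteral analgesic from outside those classes has no counted event, so the record shows sufficient relief.

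The documents themselves supply one such drug. IV lidocaine is neither an opioid nor an NSAID. Read literally, hydromorphone given outside the protocol makes the patient a failure, while lidocaine given outside the protocol does not. That asymmetry is awkward in a trial that compares these two drugs.

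At stake is the meaning of the first-listed secondary efficacy outcome: the success proportion in each arm, and possibly the difference between arms.

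**Working it through.** **1. The plan's own figure.** Sample size calculation: difference 1.3, SD 2.8, alpha 0.05 (two-sided reproduces the figure), power 0.80.

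n = 2 × (1.96 + 0.84)² × 2.8² / 1.3² ≈ 73 per group. Then 146 × 1.05 = 153.3, rounded up to 154, or 77 per arm.

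The stated 73 and 154 reproduce. They concern the primary outcome and do not depend on this point. The plan gives no figure for secondary outcome 1.

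**2. How the rule scores each kind of patient.**

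| Parenteral rescue received | Concept | Scored |
|---|---|---|
| None | success | success |
| Opioid or NSAID, with or without another drug | failure | failure |
| Only an analgesic outside the two classes | failure | success |

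Only the last row disagrees, and always in the same direction. The omission can raise an arm's success rate but cannot lower it.

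**3. Illustration of size.** The documents give no rescue rates and no mix of rescue drugs, so every rate here is assumed. Let r be the true share of an arm receiving any parenteral analgesic rescue, and m the share of those patients who receive only an unlisted drug.

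- Scored failure: p = r(1 − m)
- Overstatement of success: r × m
- Scored difference: d = p₁ − p₂
- 95% CI: d ± 1.96 × √[p₁(1 − p₁)/77 + p₂(1 − p₂)/77]

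Take r₁ = 0.50 (lidocaine) and r₂ = 0.30 (hydromorphone), so true success is 50% v 70%.

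| m, lidocaine / hydromorphone | p₁, p₂ | Overstatement (points) | Difference (95% CI), points |
|---|---|---|---|
| 0% / 0% | 0.500, 0.300 | 0, 0 | 20 (5 to 35) |
| 5% / 5% | 0.475, 0.285 | 2.5, 1.5 | 19 (4 to 34) |
| 10% / 10% | 0.450, 0.270 | 5, 3 | 18 (3 to 33) |
| 20% / 20% | 0.400, 0.240 | 10, 6 | 16 (1 to 31) |
| 20% / 5% | 0.400, 0.285 | 10, 1.5 | 11.5 (−3 to 26) |
| 5% / 20% | 0.475, 0.240 | 2.5, 6 | 23.5 (9 to 38) |

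At 10% in both arms, the misscored patients number 0.05 × 77 = 3.9 and 0.03 × 77 = 2.3. Each one moves an arm's rate by 1/77 = 1.3 points.

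With equal shares the difference shrinks, but no interval in this range reaches zero. With unequal shares it can move either way, and in the 20% / 5% case the interval includes zero. These rows show what is possible; they do not predict what will happen.

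**The case against.** The strongest reply is that this is a definition, not an error. The plan states a concept and then says, by drug class, how it will be scored. A class list is objective and needs no judgement about why a drug was given. Under that rule nobody is misscored, and protocols often define endpoints without giving reasons. The objectivity argument stands and shapes the fix. It does not explain why the list stops at two classes, and the outcome will still be read under its stated meaning of sufficient relief.

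The second reply is that the affected patient may hardly exist. The Background passage on alternatives concerns replacing opioids in general, not rescue after study drug, and its example is the study drug itself. Clinician discretion shows that other rescue is allowed, not that it happens. The eligibility rule points towards opioid rescue: "At the time of enrollment, the ED treatment plan must include use of an intravenous opioid". The aim describes the comparison in the same spirit: "when compared to IV hydromorphone, the putative standard of care". A patient given an unlisted drug plus any parenteral opioid or NSAID is still counted. All of this stands, and it is why the effect is probably small.

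Third, a difference between arms is made less likely by blinding: "Research subjects, clinicians, and research personnel will be blinded". This stands in part. The Blinding section itself recognises that side effects particular to one arm may threaten the blind.

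A reader might infer that the list favours lidocaine, or that it could reverse the trial's conclusion. The documents support neither. They give no frequency of unlisted rescue and no reason to expect it more in one arm, and the primary outcome does not use this list.

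**Conclusion.** The point holds as a minor, cheap improvement. As written, secondary outcome 1 scores a patient rescued only with a parenteral analgesic outside the two listed classes as having sufficient relief, and non-study IV lidocaine falls in that gap. Within an arm the effect can only be to overstate success. Its frequency, and the size and direction of its effect on the comparison, cannot be derived from the documents. They may be zero and are probably small.

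The figures above rest wholly on assumed rescue rates and assumed unlisted-only shares, so they support no firmer statement. The primary outcome, the sample size of 154 and clinical care are unaffected.

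**What to change.** Before unblinding, amend the scoring sentence in item 1 so that the list continues beyond opioids and NSAIDs to any other parenteral analgesic given beyond the protocol doses, with non-study lidocaine named explicitly. Where possible, write the extension as named drugs or classes so that the rule stays objective. Score it from the off-protocol medication already to be recorded under Details of protocol. Keep drugs given for associated symptoms under item 4. Decide any drug with both uses blind to arm, by a rule written in advance. Report the opioid/NSAID-only version alongside as a sensitivity analysis, so that the effect of the wider list is visible.

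The cost is a short text change, one additional reported result, possibly one data field for indication, and a little blinded judgement on dual-use drugs. A wrong judgement of indication could lower the success rate, and the rate may be slightly lower in any case. The change affects scoring only, not what clinicians may give.

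### Pain scores at 120 and 180 minutes appear to depend on staying in the ED, and a t-test on those still scored can mislead if leaving is related to pain relief

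*Combined protocol and SAP*

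**What the plan says.** Secondary efficacy outcomes, item 2, lists "Improvement in numerical pain scores 15, 30, 90, 120, and 180 minutes after investigational medication".

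On collection, the Study design paragraph of the Methods states "Outcomes will be assessed through out the ED stay and by telephone 7 days later". Under Details of protocol, "Research associates will perform an assessment of pain and adverse events every 30 minutes". No end time is given, and nothing is said about scoring a patient who has left. The day-7 call covers satisfaction, how the pain went after the visit, and adverse events. It does not ask for a 120- or 180-minute score.

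On analysis, the Analysis section states "For formal statistical testing, we will use the ttest". It names no model across time points, no imputation and no sensitivity analysis. The intention-to-treat paragraph adds "Once an investigational medication is initiated, the patient will be included in the analysis", and goes on to cover incomplete infusions and off-protocol analgesia. It does not say how a patient without a score at a given time is handled. Missing data appear otherwise only in the Sample size calculation, as part of the reason for enrolling 105% of the required number.

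**The concern.** A t-test of improvement at 180 minutes needs a 180-minute score. If some patients have left by then, the test compares those who remain in one arm with those who remain in the other, and randomisation no longer protects that comparison. The likely reasons for leaving an ED visit for pain are not obviously neutral. The plan itself lists a change in disposition attributable to study drug as a safety endpoint (Safety endpoints, item 3), so departure could depend on arm as well as on pain.

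At stake are the only scheduled scores beyond 90 minutes. A real advantage could look as if it fades, or a difference could appear that is produced by who left. A reader of the results could not tell these apart, because the plan does not call for the number scored at each time.

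**Working it through.** **Inputs from the plan** (Sample size calculation): "we anticipate a mean improvement in 0-10 pain score of 4.9 and a standard deviation of 2.8"; smallest important difference 1.3; alpha 0.05; power 0.80; 73 per arm; 154 in total.

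**Inputs assumed**, because the documents give none of them: the share gone by 120 or 180 minutes, how strongly leaving depends on improvement, whether that differs by arm, and the correlation between scores.

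**1. The plan's figure.** n = 2 × (1.96 + 0.842)² × 2.8² / 1.3² = 72.8, so 73 per arm. 146 × 1.05 = 153.3, so 154. Both reproduce. The 5% addition helps precision. It cannot remove bias, and it is tied to no time point.

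**2. Leaving unrelated to pain.** There is no bias, only lost precision. With 20% gone, n = 73 × 0.8 = 58.4, SE = 2.8 × √(2/58.4) = 0.518, and power = Φ(1.3/0.518 − 1.96) = 0.71. With 40% gone, n = 43.8, SE = 0.598, and power = 0.58.

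**3. Leaving related to pain, one time point.** Simulation with 2 million patients per arm. Improvement is N(4.9, 2.8) in one arm and N(3.6, 2.8) in the other. The log-odds of leaving are a + b × (improvement − 4.25), with a set to give the stated overall share gone. Difference among those present, when the truth is 1.3:

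| Gone overall | b = 0 | b = 0.25 | b = 0.5 | b = 1.0 |
|---|---|---|---|---|
| 10% | 1.30 | 1.25 | 1.16 | 1.04 |
| 20% | 1.30 | 1.22 | 1.08 | 0.91 |
| 40% | 1.30 | 1.18 | 0.99 | 0.76 |
| 50% | 1.30 | 1.17 | 0.96 | 0.70 |

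If worse patients leave instead (b = −0.5, same rule in both arms), the result is also attenuated: 1.08 at 20% and 0.99 at 40%.

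**4. A leaving rule that also differs by arm.** With b = 0.5 and a shift of −1 or +1 in the log-odds of leaving for the arm with less improvement, the difference is 0.77 or 1.42 at 20% gone, and 0.52 or 1.46 at 40%. With no true difference and 30% gone, the same shifts produce a spurious difference of about 0.42 in either direction.

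**5. Repeated measures.** Here departure accumulates over the scheduled times and depends on the last recorded improvement, with correlation 0.7 and log-odds of leaving up 0.2 to 0.6 per point. The 180-minute difference among those present is:

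- about 1.26 to 1.04 with roughly 15-30% gone;
- about 1.21 to 0.93 with roughly 40-55% gone.

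A likelihood-based repeated-measures model on the recorded scores stays near 1.30. When the leaving rule also differs by arm, those present give 0.50 or 1.48 and the model again stays near 1.30. With 77 per arm, and 50-59% of the better arm and 43-44% of the other gone, the SD of the 180-minute estimate is 0.52-0.53 with the model against 0.58-0.61 with the t-test.

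**6. Where the model's assumption fails.** If departure depends on the current, unrecorded score, the model gives 1.28 to 1.10 and the t-test on those present 1.25 to 0.84. The model is closer to 1.30 but removes only part of the bias.

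**The case against.** The strongest reply is that much of the mechanism is not in the documents. A reader might infer that patients leave because they are better, so that the arm difference is certainly pulled toward zero. The plan gives no length of stay, no expected share gone and no link between relief and departure. Admission and transfer also end the ED stay. Steps 2 and 4 show that the bias can be nil or go the other way. That part of the objection stands, and the point is conditional for that reason.

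Three further inferences also go too far.

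- **No later scores at all.** The plan does not say that scoring stops at departure, nor that each time point gets its own t-test. Both are the natural reading, since no later procedure and no model across times is given.
- **Conflict with intention to treat.** That paragraph concerns incomplete infusions and off-protocol analgesia. It does not promise a score at every time.
- **The only evidence on duration.** The day-7 call asks about later pain, and off-protocol analgesia during the visit is recorded.

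On size, few departures mean little bias. In a single-exit version of step 5, 5% gone gives 1.29 to 1.22 (bias 0.01 to 0.08) and 10% gives 1.28 to 1.18 (bias 0.02 to 0.12), which is small beside a standard error above 0.5. It is also fair to say that step 5 sets departure by recorded scores, the condition under which the model is unbiased. Step 6 answers that in part.

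The objection does not remove the gap itself. The plan has no rule for a score that is absent because the patient has left, and the named test can only drop that patient.

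**Conclusion.** The point holds in conditional form. The 120- and 180-minute scores appear to depend on remaining in the ED, and the named test uses only patients who have one. If departure is related to pain relief, the comparison is no longer randomised. Better patients leaving by the same rule in both arms biases it toward zero; a rule that also differs by arm can bias it either way; departure unrelated to pain costs precision only.

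Under the step 5 assumptions, a true 1.3 becomes about 1.26 to 1.04 with moderate departure and 1.21 to 0.93 with heavy departure. The difference of 1.3 and the SD of 2.8 are the plan's. The departure rates, the slopes and the correlation are assumptions, and the documents do not show which case applies.

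The reach is limited to two time points within one secondary outcome. The sample size is unaffected and the primary outcome is not the target, although its timing (90 minutes under Outcomes, one hour under Analysis) must be reconciled separately. The change is worth making because it is cheap and the model does better than the t-test in the departure scenarios tested where leaving depends on pain.

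**What to change.** For secondary outcome 2, replace the t-tests with one mixed model for repeated measures that uses all scheduled pain scores: arm, time, arm-by-time, unstructured covariance. Take the arm difference with its 95% CI at each time from that model. Report the number of patients with a score at each time, by arm.

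Add a simple sensitivity analysis for departure that depends on unrecorded pain, for example shifting the unrecorded improvement of departed patients by a stated range, separately by arm.

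A pain score could also be recorded at ED departure, when the blinding guess is already asked. It falls at an irregular time and has no place in an unstructured model over fixed times, so the rule for using it must be stated, for example only in the sensitivity analysis, carried to the next scheduled time.

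The cost is analysis wording, one table and, if adopted, one question at an existing contact. The downside is small: the model is slightly more complex than a t-test, assumes departure is explained by arm and recorded scores, and removes only part of the bias when it is not.
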